9.1 Baseline

The following demographic and baseline characteristics will be described:

- Patient characteristics, additionally subgrouped by WCD indication:
 - Gender
 - Age
 - BMI

- Heart rate at rest
- Most recent LV-EF value
- LV-EF in groups
 - ≤ 25%
 - > 25% ≤ 35%
 - > 35% ≤ 45%
 - > 45%
- and
 - < 30%
 - >= 30 – 35%
 - > 35%
- NYHA classification for heart failure
- ICD removal
- Currently implanted cardiac pacemaker
- WCD indication
- Medical history, additionally subgrouped by WCD indication
 - Documented atrial fibrillation
 - Coronary heart disease
 - Myocardial infarction
 - PCI (intervention e.g. balloon, stent, not only angiography)
 - Bypass surgery (CABG)
 - Heart failure (ever classified as NYHA II - IV)
 - Cardiomyopathy, divided into dilated, non-ischemic cardiomyopathy (DCM) or hypertrophic cardiomyopathy (HCM)
 - Congenital heart disease
 - Cardiac valve disease, divided into aortic or mitral valve disease
 - Hospitalisation during the last year due to aggravation of heart failure
 - Cardiac arrest or resuscitation
 - Inherited arrhythmia syndrome by type
 - Previous renal disease requiring therapy
 - Stroke
 - Syncope
- Current cardiovascular symptoms, additionally subgrouped by WCD indication
 - Angina pectoris
 - Chest pain
 - Increased heart rate
 - Nausea
 - Palpitations

- Shortness of breath
- Sweating
- Weakness, dizziness
- Other current cardiac symptoms
- Current medication:
 - Antiarrhythmics (amiodarone, flecainide, sotalol, other)
 - Oral anticoagulants
 - Antiplatelet agents
 - Beta blockers
 - Diuretics
 - IEC/ARA2
 - Statines
- WCD activation/programming, additionally subgrouped by WCD indication
 - WCD activation
 - Prescription period
 - Shock energy of first shock
 - VF threshold heart rate
 - VT shock delay
 - VT threshold heart rate
- Patient questionnaires:

All patient questionnaire data will be included in the analysis as long as the patient answered at least one item on the survey. In other words, no exclusion criteria will be used based on survey response completeness. Overall statistics will be presented for survey data results including

- overall response rate, i.e. availability of surveys of prospective patients in %
- item level response rate, i.e. availability of items in % and
- survey responses for all items, i.e. frequency of answers per item in %

For the majority of items in the questionnaires patients were asked to indicate their agreement using the 5-point Likert agreement response scale (strongly agree, agree, neither agree nor disagree, disagree, strongly disagree) with the following topics regarding their use of the LifeVest:

- Peace of mind
- Worry
- Sleep quality
- Confidence returning to activities of daily living (screened)
- Confidence to exercise or perform cardiac rehabilitation (screened)
- Taking condition seriously
- Improved self-care
- Confidence in LifeVest.

9.2 Follow-up data (wearing period) of ITT population

The following follow-up data will be described:

- Serious adverse events since inclusion by number of events in groups of
 - Type of event
 - Cardiac arrhythmic
 - Cardiac non-arrhythmic
 - Vascular non-cardiac (including stroke)
 - Cardiovascular without clearly defined other cause
 - Non-cardiovascular
 - Related hospital stay/prolongation of existing hospital stay
 - Causal relationship to WCD
 - Intensity
 - Outcome
 - Criteria for seriousness
- Time to first hospitalization
- Death
 - Cardiovascular
 - Cardiac
 - Vascular non-cardiac (including stroke)
 - Cardiovascular without clearly defined other cause
 - Non-cardiovascular
 - Death during prescription duration
 - Death while wearing the WCD
 - Death related to arrhythmic event
 - Death related to WCD dysfunction
- WCD events

WCD events/patients with WCD events with following event parameters:

- Type of event
- Termination of event
- Response button pressed
- Shock delivered
- Shock appropriate/inappropriate
- Occurrence of technical and non-technical problems during the wearing period
- Return of WCD device (end of therapy) due to:
 - Death
 - ICD implantation
 - Heart transplantation

- LV function improvement
- Patient's wish
- Other reason
- Clinical status on WCD return: Most recent LV-EF value, NYHA classification, risk assessment and if patient is still listed for heart transplantation
- Planned therapy after wearing period:
 - ICD implantation
 - PCI (Angioplasty, Stent)
 - Bypass surgery
 - Implantation of cardiac pacemaker
 - Heart transplantation
 - Implantation LVAD (left ventricular assist device)
 - Therapy with anti-arrhythmic agents
 - Other planned cardiac therapy
- Medication on WCD return

10. Primary analysis on ITT population

1. **Appropriate shocks** as measured by shocks delivered for adjudicated sustained ventricular tachycardia (VT) or ventricular fibrillation (VF) episodes.

- Quantitative analysis of appropriate shocks
- Analysis of the risk of not receiving appropriate shocks when necessary, calculated as number of non-terminated VT/VF events without shock delivery and without response button pressed/ number of VT/VF events

2. **Inappropriate shocks** as measured by shocks delivered for all episodes that are not adjudicated as sustained VT or VF episodes.

- Quantitative analysis of inappropriate shocks
- The risk of receiving an inappropriate shock, calculated as number of inappropriate shocks/ non VT/VF events

11. Secondary analysis on ITT population

Overall survival as measured by the ratio of the number of patients that are alive at the end of the use of the WCD compared to the total ITT population.

Survival analysis using Kaplan-Meier curves and cox proportional hazard models will be performed to identify impacts on survival and the occurrence of WCD events will be displayed in tables in the following subgroups :

- indication for the WCD,
- medical history, and
- disease etiology: heart failure according to ESC guidelines
 - no HF (LV-EF $\geq 50\%$)

- intermediate HF (LV-EF $\geq 40 - < 50\%$)
- HF (LV-EF $< 40\%$)

12. Efficacy and safety analysis on ITT population

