7.2 Dataset for interim analysis

An interim analysis is planned for reimbursement dossier renewal latest in September 2018. For this purpose a dataset for interim analyses will be generated at a specific point in time defined by the sponsor. The dataset for interim analysis is a data snapshot and will partially consist of uncleaned data because data documentation and cleaning are ongoing at this point in time.

8. General methodology

Continuous variables will be summarized as means (standard deviations [SDs]), quartiles (25 %, 50 % and 75 %), and minimum and maximum value. The number and percentage of patients in each category will be presented for nominal variables. For graphical representation distribution plots, histograms, boxplots and bar charts will be used, as appropriate.

Comparisons of continuous variables will be performed using the Student’s t-test and if assumptions are not met Wilcoxon rank-sum test, and comparisons of nominal variables will be performed using the Pearson’s chi-square test or Fisher’s exact test, as appropriate.

For time-to-event data, the Cox proportional hazards model will be used unless specified otherwise. Survival estimates will be illustrated in Kaplan-Meier plots.

For comparing groups with respect to binary outcomes, logistic regression or analysis of covariance (ANCOVA) will be used as specified.

Statistical comparisons will be performed using two-sided significance tests with alpha=0.05 unless otherwise noted.

9. Demographics and characteristics of ITT population

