12.2 Secondary parameters

- Analysis of primary outcome parameters (section 12.1) in sub-groups according to their clinical profile at baseline:
 - Age:
 - < 40 years
 - $\geq 40 - < 65$ years
 - $\geq 65 - < 75$ years
 - ≥ 75 years
 - Gender
 - Indication of WCD:
 - implantable cardiac defibrillator (ICD) removal due to cardiac device infections,
 - a bridge to heart transplantation,
 - in the early post-MI period with left ventricular (LV) dysfunction (LVEF $< 30\%$),
 - a recent coronary revascularization with LV dysfunction (LVEF $< 30\%$).
 - Type of inherited arrhythmia syndrome:
 - Long-QT syndrome (LQTS)
 - Brugada syndrome
 - Catecholaminergic polymorphous ventricular tachycardia (CPVT)

- Arrhythmogenic right ventricular cardiomyopathy
- Other
- Unknown

In addition the following parameters will be analysed in the mentioned subgroups:

- Cause of death (as assessed by CEC)
- Hospitalization
- Type of SAE

LV-EF at baseline and at time of WCD end of use

13. On-treatment efficacy analysis

For on-treatment efficacy analysis, tables on baseline characteristics and outcome will be shown comparing patient group on-treatment to not on-treatment (for definitions refer to 6.3).

14. Analysis of WCD usage on ITT population

Analysis of usage patterns will be done by:

- Description of WCD wearing profile:
 - Average prescription period
 - Average wearing period (date of activation to date of end of use)
 - Average wearing period by gender
 - Description and analysis of compliance of WCD wearing: WCD device in use during wearing period (days in use / number of days of wearing period) Average daily WCD usage (hours)
- Regression model/ANOVA evaluating factors influencing the non-compliance of patients with prescribed WCD (age, gender, neurologic function, co-morbidities etc.)
- Distribution of reasons for end of WCD usage
- Kaplan-Meier curves for time to end of WCD usage.

15. Missing values

Missing data will not be replaced by any algorithm.

16. Applied software

R (version 3.3.3 or later)

17. Literature

- 1) Myerburg RJ. Sudden cardiac death: exploring the limits of our knowledge. *J Cardiovasc Electrophysiol* 2001; 12:369-81.

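### SAP 9.2 counts serious adverse events by event only, so the plan as written does not yield the percentage of patients with each type of SAE or with a device-related SAE

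*Combined protocol and SAP*

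**What the plan says.** SAP 9.2 opens with "The following follow-up data will be described" and gives the SAE item as "Serious adverse events since inclusion by number of events in groups of" six attributes: type, related hospital stay or its prolongation, causal relationship to the WCD, intensity, outcome and seriousness criteria. Further down, the device-event item reads "WCD events/patients with WCD events with following event parameters". Two other safety items in 9.2 are patient-level: deaths, split by cause, and "Time to first hospitalization".

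SAP 8 sets the general rules. For summaries: "The number and percentage of patients in each category will be presented for nominal variables". For tests: "comparisons of nominal variables will be performed using the Pearson’s chi-square test or Fisher’s exact test, as appropriate", and "Statistical comparisons will be performed using two-sided significance tests with alpha=0.05 unless otherwise noted". It names no method for repeat events in one patient.

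SAP 12.2 returns to SAEs by subgroup (age, gender, WCD indication, type of inherited arrhythmia): "In addition the following parameters will be analysed in the mentioned subgroups". The parameters are cause of death, hospitalization and type of SAE. Neither the counting unit nor a test is named.

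**The concern.** The authors named two units for device events and one for SAEs, so a programmer working from 9.2 would build SAE tables of events. SAEs here include hospitalizations, heart surgery or revascularization, and arrhythmic and other cardiac events (Protocol 5.3.1.4 and 12). Several of these can recur in one patient. An event count then does not tell the reader how many patients had an SAE of that type, or one attributed to the device.

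Wear time is also unequal. Protocol 5.1.1 anticipates a mean of three months, with some indications at one month, some at up to six, and transplant candidates wearing the device until transplantation or ICD implantation. Indication is one of the 12.2 subgroups, so raw counts by indication reflect exposure as well as risk.

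The safety evidence for the reimbursement renewal (SAP 4.2) is at stake. Protocol 5.1.3 lists hospitalization, cardiac events and non-cardiac events among the primary parameters to be followed.

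**Working it through.** **1. The plan's own figure.** The plan states no precision or rate for SAEs. Its only precision figure is for the shock rate: 0.8 points at 1% and 1.8 points at 5% with 550 patients (Protocol 6.1, SAP 5). The 95% half-width 1.96 × √(p(1−p)/n) gives 0.83 and 1.82 points at n = 550, so the figure reproduces. At the expected final n of about 1,200 it gives 0.56 and 1.23. Nothing here is in dispute.

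**2. Which unit applies to SAEs?**
- SAP 9.2, SAE item: events.
- SAP 9.2, device-event item: events and patients.
- SAP 8, general rule for nominal variables: patients.
- SAP 12.2, hospitalization and SAE type: not stated.

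SAP 8 is a default, while 9.2 is specific to SAEs and names a different unit. Type, causality and intensity are attributes of an event, and one patient can fall into several categories, so the default does not translate directly. On the text alone, 9.2 governs or the two conflict. Either way, the patient percentage is not clearly requested.

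**3. What an event count leaves open (illustration).** Assumed: N = 1,200, E = 240 SAEs, m = SAEs per affected patient. The documents give neither E nor m. Share of patients affected = E / (m × N).

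| m | Share affected |
|---|---|
| 1 | 240/1,200 = 20.0% |
| 1.25 | 192/1,200 = 16.0% |
| 1.5 | 160/1,200 = 13.3% |
| 2 | 120/1,200 = 10.0% |
| 3 | 80/1,200 = 6.7% |

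The same event total fits a range of 20.0 − 6.7 = 13.3 points. The sampling half-width of a directly reported percentage would be 1.96 × √(0.20 × 0.80/1,200) = 2.3 points at 20.0%, and 1.96 × √(0.067 × 0.933/1,200) = 1.4 points at 6.7%.

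**4. Unequal wear time (illustration).** Take two subgroups with the same constant SAE rate per month, one worn for one month and the other for six, the ends of the range in Protocol 5.1.1. Expected SAEs per patient differ by 6/1 = 6-fold with no difference in risk. Subgroup means will lie closer together, so this is an upper bound within that range.

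**5. If someone did test event counts as independent (conditional).** With design effect D = 1 + (m − 1)ρ, where ρ is the assumed within-patient correlation, a nominal 5% two-sided test has actual level 2 × (1 − Φ(1.96/√D)).

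| m | ρ = 0.2 | ρ = 1.0 |
|---|---|---|
| 1.25 | D = 1.05, 5.6% | D = 1.25, 8.0% |
| 1.5 | D = 1.10, 6.2% | D = 1.50, 11.0% |
| 2 | D = 1.20, 7.4% | D = 2.00, 16.6% |

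A simulation gives the same direction. It used 10,000 runs, two subgroups of 600, a mean of 0.2 SAEs per patient and no true difference. Comparing event totals rejected in 5.2% of runs without overdispersion, and in 7.2%, 12.3% and 18.4% with gamma dispersion of 1, 3 and 6. Comparing the proportions of patients with at least one SAE rejected in 4.8% to 5.1% throughout.

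**The case against.** The best defence has four parts.

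- **The gap is narrower than it looks.** Deaths occur at most once per patient. Time to first hospitalization is patient-level by construction, and with the Kaplan-Meier method of SAP 8 the cumulative proportion hospitalized can be read off. Device events already carry patient counts. A reader might infer that the plan gives no patient-level safety result at all, and that is wrong. What remains missing is the patient percentage by SAE type, causality, intensity, outcome and seriousness.
- **No faulty test is planned.** A reader might infer that the subgroup tests will treat repeat events as independent. The documents do not say so: 9.2 is descriptive, 12.2 names no unit or test, and SAP 8 offers its tests only where appropriate, in a section that counts patients. Step 5 shows a risk left open, not a planned error.
- **An event table is not wrong.** It correctly reports a different quantity. A reader might want to state by how much it overstates incidence, but without an SAE rate or a repeat rate in the documents no such percentage can be supported. Participation averages about three months (Protocol 5.2.8), which limits repeats.
- **The study is descriptive, and its primary objectives are shocks.** This stands, and it limits the weight of the point.

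The SAP 8 patient rule does not settle the matter, because the more specific SAE line in 9.2 names another unit.

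**Conclusion.** The point holds as a gap in the safety tables. Followed as written, SAP 9.2 gives SAE counts by event. Outside deaths and first hospitalization, it does not give the percentage of patients with at least one SAE of each type or with a WCD-related SAE. Raw counts in the 12.2 subgroups would mix repeat events and unequal wear time. Inflated test error arises only if the SAP 8 tests are applied to event counts, which the SAP neither plans nor excludes.

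The size cannot be fixed from the documents. The 6.7% to 20.0% range rests on an assumed 240 SAEs in 1,200 patients and one to three SAEs per affected patient. If repeats prove rare, the event and patient tables will nearly agree, but the exposure problem by indication would remain. The change is worth making because the study exists partly to supply safety data and the remedy is almost free.

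**What to change.** In SAP 9.2 and 12.2, report for every SAE category:

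1. the number of events;
2. n (%) of patients with at least one event, with a 95% confidence interval, using the SAP 6.1 population as denominator;
3. events per 100 patient-months of wear.

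Item 2 does not remove differences in wear time, so items 2 and 3 are both needed by indication. Add a note that a patient may appear in more than one category, so that patient counts need not sum to the total.

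In SAP 12.2, state that the patient is the unit for any subgroup comparison of SAEs or hospitalization. In SAP 8, add that the chi-square and Fisher tests are not applied to event counts.

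The cost is a few extra table columns from data already in the e-CRF and the device's wear record. No new data are collected, and the shock analyses in SAP 10 do not change.

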5.1.3 Main Definitions and criteria for evaluating efficacy and safety

Efficacy will be evaluated using the success rate of appropriate shocks. In order for a shock to be appropriate, it must be administered while a patient is experiencing either sustained VT or VF. Otherwise, the shock is inappropriate.

The risk associated with the use of LifeVest will be assessed in terms of inappropriate shocks. Any shock administered to a patient who is not experiencing either VF or sustained VT at the time of administration is an Inappropriate Shock. Even if the patient experiences VT or VF and the condition resolves by itself or bystanders intervention just prior to administration of the shock, it would be classified as Inappropriate.

The classification of individual shocks into the categories of Appropriate and Inappropriate is quite unambiguous, so long as the ECG signal is of sufficient strength to be able to accurately determine the heart rhythm. If the signal is obscured by noise and it is not possible to unambiguously determine the rhythm the shock is generally categorized as Inappropriate, because the noise is generally the cause of the false detection.

All appropriate and inappropriate WCD shock deliveries, as well as VT/VF events will be recorded and analyzed by means of precise ECG recording, provided the VT/VF exceeds the programmed rate threshold for event detection by the WCD. ECG recordings are retrievable from a central server to which all WCD data and ECGs will be transmitted automatically. Similarly, all shock-withhold VT/VF events or VT/VF events that terminated spontaneously will be recorded and counted. All potential bradyarrhythmic or asystole events will be recorded. The device is programmed to record events which are slower than 20 beats per minute or have a QRS amplitude less than 200 microvolts (peak to peak), provided the patient does not respond to alarms.

There will be assessment of all ventricular tachyarrhythmic events, either treated by WCD-shock or with shock withheld by the patient. Furthermore, the assessment of the overall outcome (death) and of clinical events (cardiac and non-cardiac), such as hospitalization, heart failure status, ischemic events, ICD implantation, Pacemaker implantation, surgical interventions (CABG or valve replacement) during the period of WCD wearing.

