5.3.1.5 Data extracted from the LifeVest Network

- Wear time (hours per day)
- Description of all delivered treatments and associated ECG
- Description of asystole, detected arrhythmia with no treatment (e.g., short run of VT) and associated ECGs
- Information about any technical malfunctions and misuses, if applicable

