The patient will in any case receive detailed training on the use of the WCD by the ZOLL Company personnel. This will give the patient the opportunity to raise further questions about the device and data handling to the ZOLL personnel and the responsible physician.

12. Adverse events, adverse device effects and device deficiencies

Serious adverse events, i.e. cardiac and non-cardiac death, hospitalization, heart surgery, will be documented in the e-CRF. Adjudication of SAEs and second assessment of safety aspects will be performed by the sponsor.

Non-serious adverse events and adverse device effects as well as serious adverse device effects and other device deficiencies, as defined by good clinical practice and other relevant regulations, will be reported according to clinical routine procedures. For all legal reporting requirements, the sponsor remains fully responsible in the frame of his regular routine processes of reporting concerning his market authorization. Therefore, the sponsor's assessment and reporting responsibilities are not affected by this study.

13. Clinical Event Committee

The Clinical Event Committee will be composed of three experts. These experts will adjudicate, in an independent blinding manner, the occurrence of treatments and their classification (appropriate/inappropriate shocks), and will review the detected arrhythmia where no treatment was given.

14. Study limitations

Study limitations include mainly the observational nature of the design and the lack of control group.

The number of included patients could also be a limitation. As the study will start along with the early-stage launch of LifeVest, the number of patient inclusions will depend on the commercialization activities and is expected to increase over time.

15. Quality control & Quality assurance

The accuracy and completeness of the CRF entries will be monitored and checked against source documents according to a risk based monitoring plan.

Quality control procedures will be implemented to ensure the relevance and consistency of datasets.

16. Publication policy

16.1 Statement indicating whether the results of the clinical investigation will be submitted for publication.

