4.1 Primary study objectives

1. **Appropriate shocks** as measured by shocks delivered for adjudicated sustained ventricular tachycardia (VT) or ventricular fibrillation (VF) episodes.
2. **Inappropriate shocks** as measured by shocks delivered for all episodes that are not adjudicated sustained VT or VF episodes.

The frequency and rate of appropriate and inappropriate shocks will be measured. The risk of receiving an inappropriate shock will be analyzed. The risk of not receiving appropriate shocks when necessary will also be analyzed.

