Between August 2016 and April 2018, 1,110 patients were expected to receive LifeVest in clinical routine. Considering a participation rate of 50 % related to centers participating in the study and consent given, around 550 patients were considered to participate in this study.

Due to an observed recruitment rate exceeding the initial expectations, the recruitment goal was reached prematurely with an estimated enrollment of about 1,200 patients until 31st March 2018. After the end of recruitment, follow-up of patients is planned until 31st march 2019 (LPLV).

According to most recent data from literature, the frequency of ventricular tachyarrhythmic events with shock delivery within the spectrum of indications for the LifeVest device and within the associated wearing periods was estimated between 1% and 5% [6]. In this present study, a population of 550 patients was expected as primary assumption, allowing to observe a shock delivery rate ranging between 1%-5% with an absolute precision below 2% (0.8 for 1% and 1.8 for 5%). This sample size was considered to be statistically sufficient to answer the pre-defined research questions, however, the expected final population in the study of about 1,200 patients will increase the level of precision.

6. Analysis populations

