12.1 Primary parameters

- Arrhythmic (VT/VF) events and characterization of event:
 - Number of WCD shocks until termination of the tachycardia event
 - Cardiac arrest immediately after shock delivery
 - Asystole after VT/VF event
 - Maximum heart rate during ventricular tachycardia
 - Polymorphic VT event
 - Immediate ventricular fibrillation (VF)
 - Ventricular tachycardia degenerating into ventricular fibrillation (VF)
- Efficacy will be evaluated using the success rate of appropriate shocks: Number of VT/VF events terminated by shocks/VT/VF events with shock delivery
- Rate of treated VT/VF episodes calculated as shocked VT and VF events/ all VT and VF events
- Cumulative probability of sustained VT/VF, determined according to the Kaplan-Meier method in function of time
- Number of arrhythmic events and shocked events
 - Within 30 days from activation date
 - Within 90 days from activation date

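### SAP 10, item 1: the ratio labelled as the risk of no appropriate shock when one was needed keeps unshocked self-terminated and button-press events in its denominator, so it is too low for its label when there are both missed shocks and such events

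*Combined protocol and SAP*

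**What the plan says.** SAP 4.1 and protocol 4.1 both include this quantity in the primary objective: "The risk of not receiving appropriate shocks when necessary will also be analyzed". Neither document defines when a shock is necessary. The only formula is in SAP 10, item 1, where the risk is "calculated as number of non-terminated VT/VF events without shock delivery and without response button pressed/ number of VT/VF events".

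Other places show which events the plan will have in hand:

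- Protocol 5.1.3 states that "all shock-withhold VT/VF events or VT/VF events that terminated spontaneously will be recorded and counted".
- Protocol 5.3.1.5 extracts from the device network "detected arrhythmia with no treatment (e.g., short run of VT) and associated ECGs".
- Protocol 13 says the Clinical Event Committee (CEC) "will review the detected arrhythmia where no treatment was given".
- SAP 9.2 lists, for each WCD event, its type, termination, button press, shock delivery and shock appropriateness.

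SAP 12.1 shows a denominator that is restricted explicitly. The shock success rate is "Number of VT/VF events terminated by shocks/VT/VF events with shock delivery".

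**The concern.** The label describes a conditional risk: among events that needed a shock, how often none was given. The numerator follows that idea. An event that stopped by itself, or in which the patient pressed the response button and no shock followed, is not counted as a missed shock. The denominator does not follow it, because those same events are still counted among the events at risk. An event treated as not needing a shock above the line should not dilute the risk below it.

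The figure belongs to the primary objective of a study that is meant to supply efficacy and safety data for the reimbursement dossier (protocol 1.4, SAP 4.2). Two cohorts with the same record of missed and delivered shocks would report different risks if one simply had more self-terminating or withheld episodes. Where the mismatch has an effect, it favours the device.

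**Working it through.** **Inputs.** The documents give no counts of VT/VF events and no planned value for this ratio, so there is no figure of the plan's own to reproduce. The only anchor is SAP 5, which puts "the frequency of ventricular tachyarrhythmic events with shock delivery within the spectrum of indications for the LifeVest device" at 1% to 5% and expects about 1,200 patients. Assuming one shocked event per affected patient, s = 1,200 × 1% = 12 to 1,200 × 5% = 60. The values of m and u are assumed.

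**Partition of VT/VF events.**

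- m: not terminated, no shock, no button press (the SAP numerator)
- s: appropriately shocked
- u: no shock, and either self-terminated or withheld by button

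The worked figures assume three things: no unshocked event was ended by outside intervention, no event had both a button press and a shock, and no shock was given only after the rhythm had resolved.

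**Formulas.**

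- SAP ratio: m/(m+s+u)
- Ratio implied by the SAP's own numerator: m/(m+s)
- Implied ratio divided by SAP ratio, for m > 0: (m+s+u)/(m+s) = 1 + u/(m+s)

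The factor exceeds 1 only if u > 0. If m = 0, both ratios are 0%. If u = 0, they are identical.

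**Example, m = 2 and s = 40 (exact Clopper-Pearson 95% intervals).**

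| u | Ratio | 95% CI | Factor |
|---|---|---|---|
| 0 (also the implied ratio) | 2/42 = 4.8% | 0.6–16.2% | 1 |
| 10 | 2/52 = 3.8% | 0.5–13.2% | 1 + 10/42 = 1.24 |
| 20 | 2/62 = 3.2% | 0.4–11.2% | 1 + 20/42 = 1.48 |

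**Range over the anchor, m = 1 or 2.**

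- u = s/4: from 1 + 3/14 = 1.21 (s = 12, m = 2) to 1 + 15/61 = 1.25 (s = 60, m = 1)
- u = s/2: from 1 + 6/14 = 1.43 to 1 + 30/61 = 1.49

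**Opposite convention.** Suppose all u events were instead treated as needing a shock, in both places. The ratio becomes (m+u)/(m+s+u), which is never below the SAP value. The SAP ratio is therefore a lower bound under either consistent treatment.

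**Withheld events that persisted.** If some of the u events were withheld by button but did not stop, and are counted as needing a shock in both places, the example becomes (2+2)/(2+2+40) = 4/44 = 9.1% with two such events, or (2+5)/(2+5+40) = 7/47 = 14.9% with five. The undefined word 'necessary' can thus matter more than the denominator.

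**The case against.** The best defence is that the formula is explicit, nothing else in the documents contradicts it, and it can be read as a share per event: of all VT/VF events, the fraction that ended in a needed but missed shock. A denominator fixed at event onset is coherent, whereas the restricted one conditions on what happened afterwards. That is fair as a description of the number, but it calls for a different label. It does not make the number a risk conditional on a shock being necessary.

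Second, the item heading in SAP 10 refers to adjudicated sustained VT or VF, and SAP 12.1 says all VT and VF events where it means all. If the heading governs, short runs of VT drop out and protocol 5.3.1.5 lends no support. This objection stands in part: u becomes smaller. It does not become zero by definition, because a sustained episode can still stop by itself or be withheld by button.

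Third, SAP 9.2 and 12.1 already report most of the components. They do, but the cross-tabulation needed to rebuild the conditional ratio is not promised.

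Three stronger readings are tempting and are not supported:

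- A reader might infer that any missed shock makes the SAP figure too low. It does not; u must also exceed zero.
- A reader might infer that every terminated event is wrongly kept in the denominator. Events terminated by an appropriate shock belong there, since a shock was needed and given. Only events that ended without a shock, or were withheld without one, are misplaced.
- A reader might infer a material bias in the final result. The documents give no counts from which to establish one.

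**Conclusion.** The point holds as a mismatch between label and formula in a primary-objective figure. Its direction is fixed whenever it operates, and it operates only with at least one missed event and at least one unshocked self-terminated or withheld event in the denominator. Protocol 5.1.3 plans to count events of the latter kind.

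The size is unknown. Under the assumed counts, the understatement is a factor of about 1.2 to 1.5 for u between a quarter and a half of s. In the main example the shift is 1.6 percentage points at most, with heavily overlapping intervals. The ratio m/(m+s) is the target implied by the SAP's numerator; because 'necessary' is undefined, it is not the only defensible one.

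The study is descriptive and sets no test or threshold on this ratio, so no decision rule is affected. This should be fixed before the figure is reported, as an error of estimand and labelling.

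**What to change.** In SAP 10, item 1:

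1. State that 'non-terminated' means not spontaneously terminated. Without this, an unshocked event ended by outside intervention could be outside the numerator and inside the denominator, which would recreate the mismatch. Treat such events the same way in both places.
2. Set the denominator to CEC-adjudicated sustained VT/VF events that were appropriately shocked, plus non-terminated events with no shock and no button press. The numerator is the second group. Under protocol 5.1.3, a shock given after "the condition resolves by itself or bystanders intervention just prior to administration of the shock" is inappropriate, so that event does not count as appropriately shocked.
3. Keep the all-events ratio only under the label 'per VT/VF event', with the counts of self-terminated and withheld events beside it.

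Two additions are optional: an exact 95% interval with the number of patients contributing events (the interval treats events as independent), and a sensitivity ratio that counts withheld events that persisted as needing a shock, above and below the line.

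The cost is close to wording only, because SAP 9.2 already lists the event parameters. Its termination item has no stated categories, so spontaneous and external termination may need to be separated there. Where u > 0 the denominator is smaller and, if m > 0, the figure is less favourable. Any interval would also be wider: 0.6–16.2% instead of 0.4–11.2% in the example with u = 20.
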